6.0 STUDY PROCEDURES

6.1 Screening/Baseline Procedures

Assessments performed exclusively to determine eligibility for this study will be done only after obtaining informed consent. Assessments performed for clinical indications (not exclusively to determine study eligibility) may be used for baseline values even if the studies were done before informed consent was obtained.

All screening procedures must be performed within 30 days prior to registration unless otherwise stated. Baseline procedures to be completed prior to radiotherapy. The screening procedures include:

- 6.1.1 Informed Consent
- 6.1.2 Medical history
- 6.1.3 Review subject eligibility criteria
- 6.1.4 Physical exam: To include ascites and encephalopathy
- 6.1.5 Performance status
- 6.1.6 Baseline adverse event assessment
- 6.1.7 Hematology: CBC
- 6.1.8 Serum chemistries: Comprehensive metabolic panel (CMP) to include: albumin, alkaline phosphatase, ALT, AST, BUN, creatinine, electrolytes (sodium, potassium), glucose, and total bilirubin.
- 6.1.9 Coagulation assessment: PT/INR
- 6.1.10 Tumor assessment: The longest dimension of each tumor to be treated will be measured and recorded either on the most recent diagnostic scan or simulation scan.
- 6.1.11 Indocyanine green or ALBI baseline testing: ICG retention or ALBI will be measured by blood test after study enrollment and prior to radiotherapy.
- 6.1.12 Blood draw for correlative studies after study enrollment and prior to radiotherapy. See Section 10.0 for details.
- 6.1.13 For patients who consent to this portion of the study, tumor biopsy will also be performed (see section 10.1.2) after study enrollment and prior to radiotherapy.

Generally, this would be performed at the time of clinically necessary fiducial placement for radiation targeting.

6.1.14 Quality of life assessment after study enrollment and prior to radiotherapy: FACT-HEP (Version 4).

6.2 Procedures During Treatment: See section 5

6.3 Follow-Up Procedures

Patients will be evaluated approximately 1 month after completion of therapy and then at approximately 3-6 month intervals until 2 years. Evaluation will include H&P, laboratories (CBC, comprehensive metabolic panel, INR, AFP if elevated at diagnosis), and liver imaging (beginning 3 months after treatment). QOL assessments will be obtained at the same intervals for 1 year. ICG or ALBI will be assessed approximately 1 and 3 months after completion of therapy. Blood and urine (when patient is able to provide) will be collected at approximately 1 and 3 months after completion of therapy. MRI will be assessed approximately 1 month after completion of therapy. This follow up schedule will adhere to standard of care clinical follow up. Therefore, missed visits and visits that diverge from this regimen will not be considered protocol deviations. MRI and ICG must be performed at the University of Michigan. However, if patients are not able to travel for all other follow up evaluations and procedures, they may have these performed by a local physician and records obtained by the study team. If patients are concurrently or previously enrolled in another research study which requires similar testing, all efforts will be made to avoid unnecessary repeat testing.

6.4 Time and Events Table

	Pre-Rx Eval ¹	Initial RT Phase	Active Treatment	
			Evaluation Period Approximately 4-6 Weeks after Initial RT Phase	Final RT phase ⁵
History, Physical Exam, Performance Status, QOL⁸	X	PS	QOL	PS
Weight	X	Once	X	Once
CBC/Platelets	X		X	
AST, ALT, Alk Phos, Bilirubin	X		X	
BUN/Creatinine	X		X	
INR	X		X	
AFP (for HCC)	X		X	
Toxicity Notation	X	Once		Once
MELD/CTP assessment	X		X	
IC-Green⁶	X		X ⁴	
Simulation	X		X	
Perfusion MRI⁹	X		X	
Tumor biopsy⁷	X			
Diagnostic CT or MRI of liver	X ²			
Chest imaging with x-ray or CT	X ³			
Plasma and serum	X		X	
Radiation Treatment (RT)		X		X

¹ From 30 days prior to signed ICF, through treatment start.

² From 90 days prior to signed ICF, through treatment start.

³ Within 1 year prior to enrollment

⁴ If a patient does not initially qualify for the final RT phase, he/she will undergo repeat IC-Green in approximately 4 weeks as a second attempt.

⁵ Patients who do not qualify for the final RT phase will not undergo any of the treatment or testing associated with that phase. The final day of the initial RT phase will be counted as the last day of treatment, and the follow up calendar will be initiated.

⁶ For patients indicated to receive IC-Green from the treating physician. If the patient was previously enrolled on any trial utilizing IC-Green (including this one), then an evaluation of IC-Green retention performed for the other trial may be used as the pre-treatment assessment for this enrollment, as long as it is within 30 days prior to initiation of this new course of RT.

⁷ Biopsy only performed if patient consents

⁸ QOL will consist of the Functional Assessment of Cancer Therapy-Hepatobiliary (FACT-HEP) version 4. As patients can be seen in a variety of clinics, and occasionally do not follow a standard clinic schedule, missed QOLs will not be reported as a protocol deviation.

⁹ Description of Perfusion MRI protocol in the appendix.

7.0 MEASUREMENT OF EFFECT

7.1 Antitumor Effect- Solid Tumors

Response and progression will be evaluated in this study using criteria similar to the international criteria set by the Response Evaluation Criteria in Solid Tumors (RECIST) Committee [JNCI 92(3):205-216, 2000]. However, rather than tracking the sum of longest diameters, *each treated tumor will be assessed individually* and the longest diameter tracked in these lesion-specific tumor measurements. Additionally, at least 4mm change is required for a lesion to be deemed to have progressed or responded. mRECIST will also be tracked where possible.³⁰

7.1.1 Definitions

Evaluable for toxicity. All patients will be evaluable for toxicity from the time of their first radiation treatment.

Evaluable for objective response. Only those patients who have measurable disease present at baseline, have completed at least the first portion of treatment, and have had their disease re-evaluated will be considered evaluable for response. These patients will have their response classified according to the definitions stated below.

7.1.2 Disease Parameters

All tumor measurements must be recorded in millimeters. The same method assessment and the same technique should be used to characterize each identified and reported lesion at baseline and during follow-up if at all possible.

Target lesions. All tumors treated with radiotherapy are considered *target lesions* and measured and recorded separately at baseline and during follow up scans.

Non-target lesions. All other tumors are considered *non-target lesions* and will not be tracked except when noted as new or progressive (either within the liver or outside of the liver) on followup scans. Measurements are not required.

7.1.3 Response Criteria

7.1.3.1 Evaluation of Target Lesions

Complete Response (CR): Disappearance of target lesion.

Partial Response (PR): At least a 30% decrease in the longest diameter (LD) of target lesion, and at least 4mm decrease, taking as reference the baseline LD.

Progressive Disease (PD): At least a 20% increase in the LD of target lesion, and at least 4mm increase, taking as reference the smallest LD recorded since the treatment started.

Stable Disease (SD): Neither sufficient shrinkage to qualify for PR nor sufficient increase to qualify for PD, taking as reference the smallest LD since the treatment started.

Note: If subjects respond to treatment and are able to have their disease resected,

the patient's response will be assessed prior to the surgery.

7.1.3.2 **Evaluation of Remote Intrahepatic Lesions:** The presence of new or growing tumors remote from previously treated tumor sites will be interpreted based on the standard criteria for the diagnosis of metastatic disease or HCC and recorded. The presence or absence of these will be tracked separately from the target lesions.

7.1.3.3 **Evaluation of Extrahepatic Lesions:** Imaging will be evaluated for the appearance of new or growing extrahepatic tumor deposits. These will be tracked separately from the target lesions and remote intrahepatic lesions.

7.1.4 **Local Control:** Local control is defined as the lack of progression of the tumors treated by RT, either by tumor size or enhancement. Progression or development of new tumors elsewhere in the liver or outside of the liver would not constitute a local control failure.

7.1.5 **Progression-Free Survival:** Progression-free survival (PFS) is defined as the duration of time from start of treatment to time of progression.

7.1.7 **Overall Survival:** Overall survival (OS) is defined as the duration of time from start of treatment to death.

7.2 Safety/Tolerability

Analyses will be performed for all patients having received at least the first part of treatment with radiation. The study will use the CTCAE version 4.0 for reporting of non-hematologic adverse events (<http://ctep.cancer.gov/reporting/ctc.html>).

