5.1.4 Adaptive radiotherapy plan for the final 2/5 of treatment. Each patient will be treated in two parts. In the first part, the dose will be determined using the current normal tissue complication probability (NTCP) model and spatial liver function considered in treatment planning. The patient's baseline and 2nd global and spatial liver function assessments will be used to individualize the second part of treatment. Based on the MRI, adjustments in the dose distribution will be made to maximize remaining liver function and target active tumor subvolumes. Accumulated data from the trial will be used to update the individualization model.

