5.2 Toxities and Dosing Delays/Dose Modifications

Patients who receive radiation treatment on this protocol will be evaluable for toxicity. Toxicity will be assessed according to the NCI Common Terminology Criteria for Adverse Events (CTCAE), version 4.0. If these toxicities occur **during treatment**, then RT will be held until resolution: Grade ≥ 3 ascites, change in ALBI score by 0.5, Child Pugh score greater than or equal to 2.

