5.3 Duration of Therapy

Therapy would typically continue until delivery of the intended number of fractions. If liver function declines after the first 3/5 of treatments and does not recover sufficiently for additional therapy, then treatment will also be considered complete after 3 fractions (see above for definition).

Treatment will also be complete if a patient voluntarily withdraws from treatment or changes in the patient's condition render the patient unacceptable for further treatment in the judgment of the investigator.

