5.4 Off Treatment Criteria

Patients will be removed from protocol therapy when any of the criteria listed in Section 5.3 apply, with documentation provided. All patients who discontinue treatment should comply with protocol specific follow-up procedures as outlined in Section 6.3. The only exception to this requirement is when a subject withdraws consent for all study procedures, loses the ability to consent freely, or is removed from follow up per the investigator's discretion, as in Section 5.6.

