5.7 Patient Replacement

Patients who do not complete the pre-treatment and post 3/5 of treatment IC Green tests or bloodwork to evaluate ALBI score, along with the initial 3/5 of treatment are considered non-evaluable and will be replaced until a total of 80 evaluable patients is reached (80 patients).

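### Section 7.2 limits safety analyses to patients who received the initial 3/5 of radiotherapy, against sections 5.2 and 7.1.1, and no section names the denominator of the toxicity rate judged against 25%

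*Combined protocol and SAP*

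**What the plan says.** Section 7.2 (Safety/Tolerability) sets the population: "Analyses will be performed for all patients having received at least the first part of treatment with radiation". Section 5.1.4 explains the term: "Each patient will be treated in two parts", the second being the final 2/5. Section 5.1.3 puts the first 3/5 in the initial phase. So the first part is the initial 3/5.

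Two other sections define the toxicity population more widely. Section 5.2: "Patients who receive radiation treatment on this protocol will be evaluable for toxicity". Section 7.1.1: "All patients will be evaluable for toxicity from the time of their first radiation treatment". Section 8.1 collects adverse events from that same first treatment. Section 7.1.1 keeps a completion condition for the response set only, namely patients who "have completed at least the first portion of treatment, and have had their disease re-evaluated will be considered evaluable for response".

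The two definitions of an evaluable patient also differ. Under section 5.7, patients who do not complete the liver-function tests "along with the initial 3/5 of treatment are considered non-evaluable and will be replaced until a total of 80 evaluable patients is reached". Section 11.2 starts from the complete prescribed treatment, then adds patients whose liver-function result ruled out the second phase and patients whom other toxicity kept from a full course. It sets no minimum dose.

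The primary toxicity endpoint in section 11.3 is a Child-Pugh rise of 2 or more within 6 months. Section 11.2 requires this in no more than 25% of patients before a phase II trial is started. Neither section names an analysis set.

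**The concern.** A safety set that requires completion of the initial 3/5 is selected on something that happens after treatment starts and that toxicity itself can cause. Section 5.3 allows treatment to end for good when changes in the patient's "condition render the patient unacceptable for further treatment in the judgment of the investigator". If that happens because of toxicity before 3/5, the patient is outside the 7.2 set and is replaced under 5.7, although sections 5.2 and 7.1.1 call the same patient evaluable for toxicity.

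The toxicity rate is a primary endpoint. It is one of the two criteria for going on to phase II, and it is to be used in designing that trial. The plan does not say which of the competing sets supplies it.

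**Working it through.** **Inputs.** Section 11.2 gives 80 evaluable patients, an expected toxicity rate of about 20%, and a limit of 25%. No section gives the number of permanent stops before 3/5, so every value for it below is an assumption.

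**The plan's own figure.** 80 × 0.20 = 16 events, as section 11.2 states. The exact 95% interval for 16/80 is 11.9% to 30.4%. The criterion is met with at most 20 events in 80 (20/80 = 25.0%).

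**Adding back omitted patients.** Let x be the events among the 80 counted patients, m the irradiated patients omitted and replaced, and t those of the m with toxicity.

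All-treated rate = (x + t)/(80 + m).

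This exceeds x/80 only when t/m > x/80. The 7.2 set therefore understates toxicity only if toxicity is commoner among the omitted patients than among those kept.

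*All omitted patients had toxicity (t = m):*

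| Events in 80 | Largest t still within 25% | Smallest t above 25% |
|---|---|---|
| 16 (20.0%) | 5: 21/85 = 24.7% | 6: 22/86 = 25.6% |
| 18 (22.5%) | 2: 20/82 = 24.4% | 3: 21/83 = 25.3% |
| 20 (25.0%) | 0: 20/80 = 25.0% | 1: 21/81 = 25.9% |

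*No omitted patient had toxicity (t = 0):* 21/80 = 26.3% fails the criterion. With four such patients added back, 21/84 = 25.0% meets it.

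*Mixed:* from 20/80, four omitted patients of whom one had toxicity give 21/84 = 25.0%, which is no change.

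**Chance of meeting the criterion, toxicity stops only.** Let p be the true all-treated rate and s the share of toxicity cases that are permanent stops before 3/5. If only these are removed, the rate in the 7.2 set is q = p(1 − s)/(1 − ps). The number omitted per 80 counted is 80ps/(1 − ps). The last column is the exact binomial chance of at most 20 events in 80 at rate q.

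| p | s | q | Omitted per 80 | P(at most 20/80) |
|---|---|---|---|---|
| 0.20 | 0 | 0.200 | 0 | 89% |
| 0.20 | 0.05 | 0.19/0.99 = 0.192 | 0.8 | 92% |
| 0.20 | 0.10 | 0.18/0.98 = 0.184 | 1.6 | 95% |
| 0.30 | 0 | 0.300 | 0 | 20% |
| 0.30 | 0.05 | 0.285/0.985 = 0.289 | 1.2 | 26% |
| 0.30 | 0.10 | 0.27/0.97 = 0.278 | 2.5 | 34% |

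This second table is one-sided by construction. Early stops without toxicity would offset some or all of the shift.

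**The case against.** The strongest reply is section 11.2 itself. The section that holds the 25% criterion counts as evaluable those whom toxicity kept from a full course, so on its wording the patient in question stays among the 80. That stands, and it means the loss follows from 7.2 and 5.7 and not from the plan as a whole. It does not settle the matter, because 5.7 calls the same patient non-evaluable and nothing says which definition governs.

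Second, section 7.2 names no endpoint, its other sentence concerns adverse-event grading, and neither 11.2 nor 11.3 refers to it. This also stands: that 7.2 governs the Child-Pugh rate is an inference. However, 7.2 is the only section that states a population for safety analyses, and 11.3 offers no other.

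Third, the route is narrow. The first part is three of five planned treatments. The calendar in section 6.4 schedules no bilirubin, INR or Child-Pugh assessment during it, and section 5.2 prescribes a hold until resolution, not a permanent stop. Patients stopped at the reassessment have already received the first part and remain in the 7.2 set. This is a good reason to expect few cases.

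Reading the first part as any radiation at all would remove the conflict, but 5.1.3 and 5.1.4 do not support that reading.

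A reader might draw three stronger conclusions that the documents do not support:

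- That the reported rate will be biased downward. This needs more toxicity among omitted than retained patients, which no section shows.
- That the interim rule and the final analysis measure one rate on different sets. The rule in section 8.7 counts radiation-induced liver disease, while the final rate counts Child-Pugh change.
- That the feasibility proportion is inflated by replacement. Section 11.3 speaks of patients, not evaluable patients, and nothing removes replaced patients from it.

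**Conclusion.** The contradiction between 7.2 and sections 5.2 and 7.1.1 is explicit, and 5.7 and 11.2 disagree on the same patient. Confidence in that textual conflict is high. It does not extend to the direction or size of any bias in the 25% decision.

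The consequence is conditional. It arises only if the 7.2 and 5.7 set is used for the Child-Pugh rate, if some patients stop for good before 3/5, and if toxicity is commoner among them than among the others. The number of such stops is unknown, probably small and possibly zero. At the expected 16/80, six omitted toxicity cases would be needed to cross 25%, and the whole shift (20.0% to 25.6%) lies inside the 95% interval for 16/80. Only close to the limit, as at 20/80, does a single case change the decision. No sample-size figure is affected. Severity is minor.

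**What to change.** Replace the population sentence in section 7.2 with wording such as: *Safety analyses will include every patient who received at least one fraction of protocol radiation, whether or not the patient was later replaced.* Name that set as the denominator of the toxicity rate in section 11.3 and of the 25% criterion in section 11.2.

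State in section 5.7 that replacement affects accrual only, so that replaced patients who started radiotherapy stay in the toxicity analysis. Then reconcile the meaning of evaluable in 5.7 and 11.2 with this.

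The cost is small. Adverse events are already collected from the first fraction (section 8.1), and follow-up after stopping is already the default: "All patients who discontinue treatment should comply with protocol specific follow-up procedures as outlined in Section 6.3". A few more 6-month Child-Pugh records would have to be obtained from standard-of-care visits. The reported toxicity rate may look slightly less favourable.

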8.0 ADVERSE EVENTS

8.1 Adverse Event Reporting Requirements

Data on adverse events will be collected from the time of the first radiation treatment through 2 years after completion of radiation. Serious Adverse Events (SAEs) will continue to be followed until:

- Resolution or the symptoms or signs that constitute the serious adverse event return to baseline;
- There is satisfactory explanation other than the study treatment for the changes observed; or
- Death.

The definitions of AEs and SAEs are given below.

Any medical condition or laboratory abnormality with an onset date before initial study treatment is considered to be pre-existing in nature. Any known pre-existing conditions that are ongoing at time of study entry should be considered medical history rather than an AE.

In addition to new events, any increase in the frequency or severity (i.e., toxicity grade) of a pre-existing condition that occurs after the patient begins treatment is also considered an adverse event if it meets the definitions below.

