8.2 Definitions

8.2.1 Adverse Event

An adverse event (AE) is any untoward medical occurrence in a patient receiving study treatment and which does not necessarily have a causal relationship with this treatment. An AE can be any unfavorable and unintended sign (including an abnormal laboratory finding), symptom, or disease temporally associated with the use of an experimental intervention, whether or not related to the intervention.

- All grade 3 and above AEs will be collected, in addition to any grade ≥ 2 gastritis, hepatic pain, vomiting, and fatigue. The NCI CTCAE v 4.0 will be

utilized to grade AEs and for AE reporting.

- Diagnostic and therapeutic non-invasive and invasive (i.e., surgical) procedures will not be reported as adverse events. However, the medical condition for which the procedure was performed must be reported if it meets the definition of an adverse event unless it is a pre-existing (prior to protocol treatment) condition or a condition entirely unrelated to the study radiotherapy (e.g. cardiac, lung, or bladder procedure).
- Abnormal laboratory values or test results constitute adverse events only if they induce clinical signs or symptoms or require therapy. They are to be captured under the signs, symptoms or diagnoses associated with them.
- When an event recurs after it is resolved, it should be handled as a new AE. However, AEs that occur intermittently can be recorded as one AE.

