9.0 DRUG INFORMATION

9.1 Indocyanine green: Indocyanine Green has FDA approval for determining hepatic function and liver blood flow. Please refer to the Package Insert for complete details.

9.2 Description: IC-GREEN™ is a sterile, lyophilized green powder containing 25 mg of indocyanine green with no more than 5% sodium iodide. It is packaged with Aqueous Solvent consisting of Sterile Water for Injection used to dissolve the indocyanine green. IC-GREEN™ is to be administered intravenously. Indocyanine green is a water soluble, tricarbocyanine dye with a peak spectral absorption at 800 nm. The chemical name for Indocyanine Green is 1-H-Benz[e]indolium,2-[7-[1,3-dihydro-1,1-dimethyl-3-(4-sulfobutyl)-2H-benz[e]indol-2-ylidene]-1,3,5-heptatrienyl]-1,1-dimethyl-3-(4-sulfobutyl)-hydroxide, inner salt, sodium salt. IC-GREEN™ has a pH of approximately 6.5 when reconstituted. Each vial of IC-GREEN™ contains 25 mg of indocyanine green as a sterile lyophilized powder.

9.3 Side effects: Anaphylactic or urticarial reactions have been reported in patients with or without history of allergy to iodides. If such reactions occur, treatment with the appropriate agents, e.g., epinephrine, antihistamines, and corticosteroids should be administered. See package insert for comprehensive list of adverse events.

9.4 Drug Interactions: No interactions with patient medications. Heparin preparations containing sodium bisulfite reduce the absorption peak of IC-GREEN™ in blood and, therefore, should not be used as an anticoagulant for the collection of samples for analysis.

9.5 Preparation and Dispensing: Under sterile conditions, the IC-GREEN™ powder should be dissolved with the Aqueous Solvent provided for this product, and the solution used within 6 hours after it is prepared. If a precipitate is present, discard the solution. The amount of solvent to be used can be calculated from the dosage form which follows. It is recommended that the syringe used for injection of the dye be rinsed with this diluent. Isotonic saline should be used to flush the residual dye from the cardiac catheter into the circulation so as to avoid hemolysis. With the exception of the rinsing of the dye injection syringe, saline is used in all other parts of the catheterization procedure.

9.6 Administration for patients indicated to receive IC-Green from the treating physician:

- 9.6.1 IC-GREEN testing will be administered according to the study calendar.

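### Adverse event collection starts at the first radiation fraction, so early harms of the protocol's own pre-radiotherapy procedures (ICG test, contrast MRI, research biopsy) fall outside it

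*Combined protocol and SAP*

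**What the plan says.** Section 8.1 sets the window: "Data on adverse events will be collected from the time of the first radiation treatment through 2 years after completion of radiation". It then deals with anything earlier: "Any medical condition or laboratory abnormality with an onset date before initial study treatment is considered to be pre-existing in nature". A further sentence reads: "Any known pre-existing conditions that are ongoing at time of study entry should be considered medical history rather than an AE". Worsening of a pre-existing condition after treatment begins does count as an adverse event.

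The definitions follow the same anchor. Section 8.2.1 describes an adverse event as "any untoward medical occurrence in a patient receiving study treatment", and Section 7.1.1 states: "All patients will be evaluable for toxicity from the time of their first radiation treatment". Section 7.2 limits the safety analysis to patients who received at least the first part of radiation.

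The protocol puts study procedures ahead of that anchor. On the baseline liver function test, Section 6.1.11 says: "ICG retention or ALBI will be measured by blood test after study enrollment and prior to radiotherapy". For patients who consent, Section 6.1.13 says that "tumor biopsy will also be performed (see section 10.1.2) after study enrollment and prior to radiotherapy". Section 5.1.1.3.1 places the first perfusion MRI in the 4 weeks before radiotherapy, and Appendix I shows that it involves a contrast injection. Section 9.3 acknowledges a known hazard of ICG: "Anaphylactic or urticarial reactions have been reported in patients with or without history of allergy to iodides".

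**The concern.** A study procedure that carries its own risk should have its harms collected from the moment it is performed. Here the clock starts later, at the first fraction, and the text labels whatever came before as pre-existing. An anaphylactic reaction at the baseline ICG test, or a bleed after the research cores, would be an event caused by trial participation that the adverse event rules do not collect.

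Safety is part of a primary objective (Section 2.1). The strategy to be carried into a randomized trial includes ICG or ALBI assessment and perfusion MRI (Section 11.1), so the trial's safety record should cover the harms of those procedures. The Section 3.2.1 exclusion for contrast allergy does not remove the ICG hazard, because Section 9.3 says reactions occur with or without an allergy history. Entry is open to patients with platelets down to 30,000/mm³ and Child-Pugh B8 and above (Section 3.1.8).

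**Working it through.** There is no figure in the plan to reproduce. The check compares the timing of each procedure with the Section 8.1 window, then asks whether another rule fills the gap.

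**Step 1: which exposures precede the window.**

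| Procedure | Scheduled times | Before first fraction |
|---|---|---|
| ICG, where used | 3 in Section 5.1.1.1.1 (baseline, mid-treatment, 1-3 months after); 4 if Section 6.3 is followed (about 1 and 3 months after) | 1 of 3, or 1 of 4 |
| Perfusion MRI | 3 in Section 5.1.1.3.1 | 1 of 3 |
| Research biopsy, optional | 1 in Section 6.1.13 | 1 of 1 |

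These are counts of procedures, not of harms. With at most one baseline ICG test and one baseline perfusion MRI per patient, 80 of each is a ceiling among the 80 evaluable patients. The real ICG number is lower to the extent that ALBI replaces ICG (Section 5.1.1.1), and tests done for other purposes may be reused (Sections 5.1.1.1.2 and 5.1.1.3.2).

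**Step 2: the same event at two times.** Section 8.2.1 collects all events of grade 3 or above, and grade 2 or above for four named terms that include hepatic pain. A grade 3 reaction at the mid-treatment ICG test lies after the first fraction and is collected. The same reaction at the baseline test lies before it and is not. Likewise grade 2 hepatic pain is collected if it starts after the first fraction, but not if it starts after the biopsy and before that fraction.

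**Step 3: does another rule catch it?**

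- *Section 6.1.6, baseline adverse event assessment.* It is listed among procedures due before registration unless otherwise stated, whereas ICG and biopsy follow enrollment. What it finds sets the baseline.
- *Section 6.4, Toxicity Notation in the pre-treatment column.* Footnote 1 lets that column run up to treatment start, so an event could be noted there. The table does not say that the note is adverse event data, and Section 8.1 would still class the event as pre-existing.
- *Section 8.4.1.* The principal investigator must hear of serious adverse events during the study whatever their cause. But a serious adverse event must first be an adverse event under Section 8.2. Section 8.2.2 also exempts hospitalizations related to pre-existing conditions rather than to the radiation.
- *Section 8.4.2.* Reporting to the IRB covers unexpected events possibly related to study treatment. Relatedness to a procedure is not mentioned.
- *Section 8.6.* It covers problems not related to an adverse event and requires them to be unexpected. An ICG reaction already listed in Section 9.3 would be hard to qualify.

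**Step 4: patients who never start radiotherapy.** Sections 7.1.1 and 7.2 leave them out of toxicity evaluability and the safety analysis. Section 5.6.2 takes patients unable to receive radiotherapy off study, and Section 5.7 replaces those who do not complete the initial 3/5 of treatment.

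**The case against.** The best defense is that the text is ambiguous rather than silent. Section 8.2.1 goes on to cover events linked in time to an experimental intervention, and Section 1.2 discusses ICG under a study-agent heading. On that reading a serious ICG reaction before radiotherapy is an adverse event and Section 8.4.1 applies. If instead it is not an adverse event, Section 8.6 opens to it, subject to its requirement that the problem be unexpected. This argument shows that the sections conflict. It does not settle the matter, because Section 8.1 names the first radiation treatment explicitly and nothing says it yields.

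Other points for the plan stand in full. The biopsy is optional and is taken during standard-of-care fiducial placement (Section 10.1.2.1), so only part of its risk comes from the research. It follows routine clinical practice, and the platelet limit is an entry criterion, not a biopsy threshold.

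Several stronger readings are tempting, and the documents do not support them:

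- *That these harms are recorded as medical history.* That sentence of Section 8.1 covers conditions ongoing at study entry, and the ICG test and biopsy follow enrollment. The harm is classed as pre-existing, but where it is recorded, if anywhere, is not stated.
- *That every biopsy harm is lost.* A complication that begins or worsens after the first fraction is captured if it meets Section 8.2.
- *That a patient harmed before radiotherapy leaves no trace.* Section 5.6 has reasons for discontinuation documented, Section 11.3 has feasibility failures investigated individually, and the monitoring committee in Section 12.0 reviews safety and retention quarterly.
- *That a primary safety endpoint is compromised.* Section 1.2 ties GI bleeding to radiation near stomach and bowel; a bleed from a percutaneous liver biopsy is not shown to be that event. Nor is it shown that such a harm is absorbed into baseline liver function, since Section 6.4 allows baseline values from 30 days before signed consent through treatment start, and they may precede the biopsy.

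**Conclusion.** The gap is real and limited. Followed as written, Section 8.1 leaves out harms of the baseline ICG test, the baseline contrast MRI and the research biopsy when they begin before the first fraction, and patients who never start radiotherapy are outside the safety analysis. Three other provisions might catch some of these events, but none clearly prevails over Section 8.1, so the passages need to be reconciled.

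The size in events cannot be stated: the documents give no rate for any of these harms, no number of patients expected to have ICG, and no biopsy uptake. Mid-treatment and later ICG tests and MRIs are inside the window. The Child-Pugh endpoint definition, the sample size of 80 and the go/no-go rule in Section 11.2 do not depend on this point. What is affected is the completeness of the safety record. The conclusion assumes that Section 8.1 is applied literally; a site that recorded procedure reactions from enrollment anyway would have a smaller gap in practice, but not under the written plan.

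**What to change.** - In Section 8.1, collect adverse events and serious adverse events related to a study-required procedure (ICG, perfusion MRI contrast, research biopsy) from the first such procedure after consent. State that these are not pre-existing. All other events start at the first fraction, as now.
- In Sections 8.2.1, 8.2.2 and 8.4.2, allow attribution to study treatment or a study-required procedure, and carry the same wording into the attribution scale in Section 8.3.2.
- Reconcile this with Section 8.4.1, and say in Section 6.4 whether the pre-treatment Toxicity Notation is adverse event data.
- Report the procedure-related events in a separate table for all enrolled patients, including those who never start radiotherapy. Keep the radiotherapy toxicity analysis anchored at the first fraction so that its denominator does not change.

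The cost is amendment wording, an earlier start date on the adverse event form, and a few more events to record. No visit or test is added.
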